At each DSMB scheduled meeting after initiation of study recruitment, SAE/AE data and a report summarizing recruitment and participant status will be prepared for review and discussion. Following its deliberations, the DSMB will issue any recommendations it may have and specify that the study should continue based upon absence of safety concerns.

After the DSMB meeting that will occur approximately nine months after participant recruitment begins, the DSMB will provide a communication summarizing SAE/AE data as well as any pertinent DSMB recommendations that may be required by the Thomas Jefferson University Institutional Review Board (IRB) or the Ethics Committees of the Indian research partners.

I. Database Management System (DMS)

Jawaharlal Nehru Medical College (JNMC) will have the responsibility for the development of an independent data management unit and utilization of the database system for the *RAPIDIRON Trial*. Data will be collected primarily with the use of paper-based forms. JNMC has successfully used the Research Electronic Data Capture (REDCap) system for numerous research projects. This system is a secure web application for building and managing online surveys and databases, and it offers a secure, privacy compliant web-based electronic data capture and maintenance system. The data are stored in a centralized system. REDCap software requires each user to have their own account and user privileges are applied to ensure that users have access only to data and information they need and are authorized to have. REDCap can be accessed from

multiple sites from any computer or mobile device, including PCs, Macs, tablets, and mobile phones.

The REDCap Website⁴¹ notes that there is a REDCap consortium which is essentially a vast support network of collaborators associated with thousands of active institutional partners in over one hundred countries. Consortium members both utilize REDCap and offer support.

The Manual of Operations for the *RAPIDIRON Trial* will discuss REDCap's important features for this research—for example, authentication procedures, data export and de-identification, data storage, security provisions and quality control measures.

J. Other Components of the Program to be Funded Independently by the Children's Investment Fund Foundation (CIFF)

A timetable for the *RAPIDIRON Trial* clinical research project is found in Appendix A. In addition to activities associated with the clinical trial discussed in this protocol, the timetable indicates that activities will be planned and data collected for related project activities that are proposed for additional funding by the *Children's Investment Fund Foundation* (CIFF) based in the United Kingdom. The activities relate to:

- A process evaluation of the research to be performed by a contracted research organization (aka Clinical Research Organization) based in India and funded externally by the Children's Investment Fund Foundation; and
- A complete medical and hematologic assessment of all study participants who require "rescue" intervention or those who are non-responders to iron supplementation.

Co-Investigator, [name], will have primary responsibility for the economic/cost-effectiveness analysis. It was determined that such an analysis could be useful for promoting scale-up of singe-dose IV iron infusions of formulations being used in the study if hypotheses for the primary outcomes are proven true.

Given the importance of distinguishing serious adverse drug reactions specifically related to intravenous iron infusions from non-serous reactions that commonly occur with the use of any intravenous medication, two experts familiar with the use of IV iron have been designated as adjudicators. Professor/[name], an expert in internal medicine and hematology who works as head of a Department of Medicine and senior physician of the hemato-oncologic clinic associated with Rabin Medical Center, Beilinson in Israel, will serve as one of the adjudicators. The second adjudicator will be [name], former President of the Federation of Obstetric and Gynaecological Societies of India (FOGSI) and currently Vice President of the Noncommunicable Diseases Division of the International Federation of Gynaecology and Obstetrics (FIGO). [name] is based at Divarkar's Specialty Hospital, Bengaluru, Karnataka, India. She is an obstetrician and women's health advocate who has 20 years of experience as a researcher. She also serves as a member of the Government of India's Anemia Committee. These two adjudicators will conduct timely reviews and provide case by case validation of all SAEs. These reports will immediately be shared with the study PI, the Chief Quality and Safety Officer, and the DSMB.

The highly qualified experts selected for the Technical Advisory Group (TAG) participated in the first official TAG meeting in June 2020. TAG members were oriented to the proposed research and provided the opportunity for discussion of the protocol prior to final refinement and issuance of the official version to be submitted for review and approval by governmental, regulatory and ethical review entities. Recommendations from TAG members have been incorporated into this protocol.

CONCLUDING STATEMENT: This research has a positive up-side without incurring significant

risk. It is designed to support and fine-tune guidelines of the Ministry of Health and Family Welfare, Government of India, to answer key questions related to clinical outcomes, and to validate the use of single-dose IV iron therapy. Further, it sets the stage for stakeholders to rapidly import and implement cost-effective programs that have enormous potential for reducing mortality and morbidity and improving the quality of life for women and children.

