Assuming a true LBW rate of 25% in the oral iron group, a final sample of 1,332 per group gives 80% power to detect a 20% relative reduction (relative risk of 0.8; 20% LBW rate in a particular IV iron group) at the alpha=0.0245 level allowing for one interim analysis when 1/3 of the information on LBW is available. With p-value boundaries of 0.000026 at the interim analysis and 0.02449 at the final analysis, based on 10,000 simulations, with complete data on 1,332 subjects per arm (444 per arm at the interim analysis), if both IV iron arms have true risk of LBW of 20%, there is a 1.6% probability of stopping early for efficacy, approximately 80% probability of concluding a particular IV arm has lower LBW risk than the oral arm, and greater than 90% probability of concluding at least one of the IV arms is better than the oral iron arm. It is projected that approximately 4,320 pregnant women will need to be randomized 1:1:1 to each of the three study arms based on assuming 7.5% missing birth weight data (due to stillbirth and other

reasons). Any one of the four research teams (based in Belagavi, Bagalkot, Raichur, or Jaipur) will enroll and randomize no more than 60% of all study participants.

With 1,332 study participants per group, we have greater than 95% power to detect differences in rates of non-anemia of at least 10% at the alpha=0.0005 level although differential rates approaching 30% are anticipated.

2. Primary Data Analysis

The primary analysis for anemia will compare each IV iron arm to the oral iron arm with respect to the percentage of participants who achieve Hb of ≥ 11 g/dL at either a 30-34 week antenatal visit or at a birthing facility based on blood collected prior to delivery using a Cochran-Mantel-Haenszel (CMH) chi-square test stratified by enrollment site (randomization stratum) at the 0.0005 level. The CMH-adjusted risk ratio and associated 99.95% confidence interval will be calculated for both comparisons. No interim efficacy analysis is planned for the anemia outcome.

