Each IV arm will be compared to the oral iron arm with respect to risk of LBW using a CMH chisquare test stratified by enrollment site at the 0.000026 level when data are available on at least 444 subjects per group (1/3 of expected information). The study will stop for efficacy if either IV arm shows significantly lower risk of LBW at the interim analysis. If the study is not stopped early, the final tests will be performed at the 0.02449 level. Stopping boundaries were calculated using a Lan-Demets spending-function approach with O'Brien-Fleming bounds. The CMH-adjusted risk ratio and associated 97.55% confidence interval will similarly be calculated for both comparisons.

The primary analysis will be performed using the intent to treat (ITT) cohort. Missing anemia and LBW data will be imputed using multiple imputation. The exact method of imputation will be specified in the statistical analysis plan prior to analysis. Fifty data sets will be imputed and the Wilson-Hilferty transformation^{30,31} will be applied to the CMH statistics fit to each data set. Results will be pooled using the method of Rubin³² to calculate the overall test of significance. The log (relative risk) estimates of each imputed data set will similarly be combined.

3. Secondary Analyses

- A. Additional Analyses of Primary Outcomes:
 - IV iron arms will be descriptively compared with respect to the rate of LBW births and rates of non-anemic patients by estimating the CMH-adjusted risk ratio and associated 95% confidence interval.
 - ii. An additional analysis comparing IV iron to oral iron will be performed on the per protocol cohort.
 - iii. An exploratory Hb-based subgroup analysis will be performed to estimate the effect of treatment on conversion to non-anemia status and the risk of LBW solely by level of Hb measured prior to randomization (between the beginning of week 14 and 17 weeks 0 days of pregnancy). Hb-based subgroups will be defined based on clinical considerations but may be collapsed depending on the sample sizes within each group.

B. Analyses for Secondary Outcomes:

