- v. If one or both of the IV iron formulations are demonstrated to be effective in transitioning women to non-anemic status (Hb ≥11g/dL) in the third trimester of pregnancy at either or both of two timepoints prior to delivery, or if one or both IV iron formulations are effective in reducing the risk of LBW deliveries, a series of secondary exploratory analyses will be performed to identify baseline factors that are predictive of treatment success. The objective of these analyses will be to support future implementation of the treatment regimen in broad populations by identifying subpopulations most likely to benefit from the treatment regimen. Separate logistic regression models will be constructed for the anemia and LBW outcomes, with predictors to include Hb levels at the time of randomization as well as TSAT and ferritin levels and other baseline characteristics identified in the Statistical Analysis Plan.

4. Interim Analysis

An interim analysis for efficacy for the LBW outcome will be performed when data are available on at least 444 subjects per group (1/3 of expected information). Using stopping boundaries from a Lan-Demets spending function with O'Brien-Fleming bounds, we set α_1 =0.000026 so that the study would stop if the comparison of either IV arm to the oral arm had p<0.000026 at the interim analysis. Assuming the observed risk of LBW is 25% in the oral arm, this would occur if the observed risk of LBW in a particular iron arm were 13.7% or less. To maintain an overall type-I error rate of 0.0245 for each IV vs. oral comparison, if the null hypothesis is not rejected at the interim analysis, the final comparisons for LBW will be completed at the 0.02449 level.

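### The exploratory models meant to show who benefits most from IV iron name only baseline predictors; as written they estimate prognosis, not the gain over oral iron

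*Combined protocol and SAP*

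**What the plan says.** Section E.3.B, item v (Analyses for Secondary Outcomes) applies if one or both IV formulations prove effective on either primary outcome. Its purpose is to support wider implementation by "identifying subpopulations most likely to benefit from the treatment regimen". The method is to "identify baseline factors that are predictive of treatment success", a term the section does not define further. Each primary outcome gets its own logistic model, specified as follows: "with predictors to include Hb levels at the time of randomization as well as TSAT and ferritin levels and other baseline characteristics". The choice of those further characteristics is left to the SAP. The section does not mention treatment arm, any arm-by-factor term, or which arms enter the fit.

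Section E.3.A, item iii separately plans an exploratory analysis to "estimate the effect of treatment on conversion to non-anemia status and the risk of LBW solely by level of Hb measured prior to randomization". That is a contrast between arms, but for Hb alone, and no interaction test is named. Section E.3.B, item i also lists Hb change within the three moderate-anemia bands among the outcomes compared across arms.

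**The concern.** The aim and the method address different quantities. Benefit is the difference between what happens on IV iron and what would have happened on oral iron. The control is active: Section D gives the oral arm treatment-frequency iron and folic acid tablets, so some of those women will also reach 11 g/dL. A coefficient for a baseline factor, fitted without an arm-by-factor term, describes who reaches the endpoint under whatever mix of arms is in the data. It cannot separate a woman who converts because of IV iron from one who would have converted anyway.

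For anemia a prognostic gradient in Hb is likely, because a woman at 9.8 g/dL needs a rise of 1.2 g/dL to reach 11 and a woman at 7.2 needs 3.8. If the factors that mark success are read as marking benefit, implementation advice could favor the women who gain least, or overlook a factor that truly changes the effect.

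**Working it through.** **Plan figures used.** Item v states no figure of its own. For LBW, Section E.1 gives 25% on oral ("Assuming a true LBW rate of 25% in the oral iron group"), 20% on IV, alpha 0.0245 and 1,332 per arm. Check, two-sided without continuity correction: n = [z(0.98775)·√(2·0.225·0.775) + z(0.80)·√(0.25·0.75 + 0.20·0.80)]² / 0.05² = [2.249·0.5906 + 0.8416·0.5895]² / 0.0025, which rounds up to 1,332. The figure reproduces and is not in dispute.

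**Illustration for conversion to Hb ≥11 g/dL.** The documents give no rates by Hb stratum, so the shares and rates below are assumptions.

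| Baseline Hb (g/dL) | Share | Oral | IV | Gain (points) | Treatment OR |
|---|---|---|---|---|---|
| 7-7.9 | 10% | 20% | 50% | 30 | 1.000/0.250 = 4.00 |
| 8-8.9 | 30% | 35% | 65% | 30 | 1.857/0.538 = 3.45 |
| 9-9.9 | 60% | 55% | 75% | 20 | 3.000/1.222 = 2.45 |

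The text does not say which arms are fitted, so the OR for 9-9.9 versus 7-7.9 was computed under each reading:

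- IV arms only: 3.000/1.000 = 3.00.
- All three arms at 1:1:1, no arm term: conversion is (2·50 + 20)/3 = 40.0% and (2·75 + 55)/3 = 68.3%, so the OR is 2.158/0.667 = 3.24.
- All three arms, arm as a main effect (2:1 IV to oral), maximum-likelihood fit to expected counts: 3.47, with a treatment OR of 2.85.
- One IV arm against oral (1:1), arm as a main effect: 3.75.

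Every reading ranks the 9-9.9 group highest for success. In the same data its gain over oral iron is the smallest on both scales.

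**Illustration for LBW.** Take one binary baseline factor split 50:50, so 666 women per cell with one IV arm and the oral arm. The half-specific risks are assumptions averaging 25% on oral and about 20% on IV. The standard error of a log OR is √Σ 1/[666·p(1−p)] over the cells involved. ORs compare the second half with the first; below 1 means fewer LBW births.

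| Case | Oral risk | IV risk | Gain (points) | Baseline-only OR, IV arm | Interaction OR |
|---|---|---|---|---|---|
| 1. Prognostic only, constant treatment OR 0.75 | 30% / 20% | 24.3% / 15.8% | 5.7 / 4.2 | 0.58 | 1.00 |
| 2. All benefit in the first half | 30% / 20% | 20% / 20% | 10 / 0 | 1.00 | 1.71 |
| 3. All benefit in the first half, factor also prognostic | 32% / 18% | 22% / 18% | 10 / 0 | 0.78 | 1.67 |

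- Case 1: the factor is flagged in the IV arm with 97% power at two-sided 0.05, although the relative effect is the same in both halves. In absolute terms the higher-risk half gains slightly more, the opposite of the group marked as success.
- Case 2: an IV-arm model misses the modifier entirely. Pooling the IV and oral arms without an arm term gives an OR of 0.75, which points to the half that gains nothing.
- Case 3: the IV-arm model leans toward the half with no benefit.

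The interaction term separates these cases. Its power is about 82% in case 2 and 77% in case 3, but both put the whole effect in one half, so smaller interactions would have less. In case 2 the standard error is 0.188, and an estimate equal to the assumed value would have a 95% interval of exp(0.539 ± 1.96·0.188), or 1.19 to 2.48.

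**The case against.** The strongest reply is that the text is incomplete rather than wrong. The predictor list is open, and part of it is deferred to the SAP. A reader might infer that the plan excludes interactions and will therefore select the wrong women. The documents do not support that: they omit arm-by-factor terms without ruling them out. Even so, the only predictors deferred are described as further baseline characteristics, so an analyst following the section would have no prompt to add arm or interactions.

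Second, Section E.3.A, item iii already estimates the treatment effect by Hb. In the anemia illustration it would show gains of 30, 30 and 20 points, so the plan does contain the means to see a reversal for Hb. This stands as a partial safeguard. It does not extend to TSAT, ferritin or other baseline factors, and nothing says which analysis guides implementation if the two disagree on Hb.

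Third, the analyses are labeled exploratory and are conditional on a positive finding. That limits the consequence and excuses imprecision. It does not make the model answer the stated question.

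Fourth, prognosis among treated women can itself inform implementation. That is true, but it is not the stated objective.

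**Conclusion.** The point holds as a mismatch between aim and specification. As written, item v would estimate who reaches the endpoint, and this may differ from who gains over oral iron. The direction of the anemia result is the same under every reading of which arms are fitted (OR 3.0 to 3.75 in favor of the group that gains least). The size rests wholly on assumed rates and shares, so the figures show that a reversal or a missed modifier can occur, not that it will or how large it would be.

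A reader might also infer that the trial's main conclusions are at risk. They are not: the primary tests, alpha allocation and sample size do not depend on this analysis. The gap that remains after Section E.3.A, item iii concerns TSAT, ferritin and the other baseline factors, and the need for a consistent answer on Hb.

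**What to change.** In Section E.3.B, item v and the SAP:

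- Fit each exploratory model in the randomized IV and oral participants together, with arm, site, the baseline factors and arm-by-factor interactions, and state which arms enter each fit.
- Report the predicted IV-minus-oral risk difference and the relative effect across each factor, with confidence intervals. Both scales are needed because a constant relative effect still gives an absolute gain that varies with baseline risk (case 1).
- Align the Hb results with Section E.3.A, item iii so that the two give one answer.
- Label any model without interactions as prognostic.
- State that the interaction estimates are imprecise and exploratory.

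The cost is SAP wording and modest extra analysis. The data are already to be collected, and no participants, visits or alpha are needed.

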iron participants will know only that they have been randomly assigned to receive an IV iron infusion without knowing the specific arm and the formulation that will be used. Further, neither the PHC staff nor the CHC infusion team will know which IV iron formulation was assigned. Rather, a pharmacist associated with each CHC performing IV iron infusions for the trial will be designated to prepare the randomly assigned IV iron formulation, per participant weight and manufacturer instructions, on the day of treatment. When a participant is to be provided an infusion at the CHC, the pharmacist will collect an infusion order from the participant. The form will have a randomization number and the participant's weight, which is needed for correct dosing. The pharmacist will match the number to randomization tables that have been provided and then prepare the correct formulation. Those who are involved with the administration of IV iron infusions for this trial will be thoroughly trained to ensure appropriate performance of their clinical and research responsibilities; this includes CHC Medical Officers and nurses who will be trained as coordinators/infusion nurses. Notably, those who will administer an IV iron infusion will be trained to ensure that it is given over an equivalent period of time consistent with package labeling for both the formulations; training will also provide instructions pertinent to an observational period recommended by both formulation manufacturers subsequent to infusion completion (of at least 30 minutes). 22,23 This time should be sufficient for recognizing and appropriately addressing drugrelated reactions should any occur as well as accurately recording data in the infusion data form.

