Assuming the study is not stopped for efficacy, one formal interim analysis for futility will be completed based on a data snapshot taken when the anemia outcome is available for 666 subjects per group (1/2 of expected information). The interim analysis for futility will involve the conditional power associated with two hypothesis tests: the two-degree of freedom CMH test of differences in prevalence of anemia prior to delivery across the three treatment arms and the two-degree of freedom test of differences in risk of LBW across the three treatment arms. If analyses for both primary efficacy outcomes show a conditional power of less than 0.2 based on the observed data at the time of the interim analysis and the assumed effect for the study design, the Data and Safety Monitoring Board (DSMB) may consider recommending that the study be stopped.

The analysis for safety will have two components. First, point and 97.5% confidence interval estimates of the risk of mortality and incidence of at least one SAE will be developed for each of the three treatment arms. If the interval estimates provide evidence that either of the active IV iron treatment arms has significantly higher risk of either mortality or adjudicated SAE incidence than the active comparator arm (oral iron), the DSMB will consider recommending stopping enrollment on that active IV iron treatment arm. In making the recommendation, the DSMB can consider the overall risk profile of the treatment arms and any evidence of efficacy that has been accumulated at the time of the interim analysis.

Additional details of the planned interim analysis will be developed in collaboration with the DSMB and the details will be included in a formal Interim Analysis Plan that will be approved by the DSMB prior to enrollment.

5. Safety Analyses

All safety analyses will be descriptive based on the safety cohort with no planned formal inference for safety. All adverse events will be summarized by system organ class by arm with point and interval estimates of the risk of each of these events estimated by either exact binomial methods or normal approximations to the binomial as appropriate for the incidence of the event. Descriptive statistics will also be generated for maternal and infant mortality and for incidence of SAEs.

6. Analysis Cohorts

- A. Intent-to-treat (ITT) cohort: All randomized study participants will be included using group assignments as randomized.

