- B. Per-protocol cohort: All study participants who receive the complete, recommended dosage of the randomly assigned IV iron formulation between the beginning of the 14th week and 17 weeks 0 days of pregnancy will be included in this cohort as will all study participants assigned to oral iron therapy who take equal to or greater than 75% of prescribed pills (as each woman given oral iron will be asked to maintain a diary indicating her pattern of use). However, use of any non-study-provided iron preparation post-randomization will represent an exclusion for the purpose of the per protocol analysis. Additionally, a participant assigned to an IV iron arm that receives only a portion of the recommended dosage for the randomly-assigned IV iron formulation will also be excluded.
- C. Safety cohort: All study participants who are randomized and receive either the provided oral iron tablets or at least some portion of the one-time, recommended dosage of the assigned IV iron formulation and who provide any safety data subsequent to treatment will be included in this cohort. For all safety analyses, these participants will be included in the analysis based on treatment actually received, not by randomization arm.

Assignment of patients into the various cohorts and treatment arms will be determined based on a masked data review prior to initiation of analyses.

F. Gender/Minority/Pediatric Inclusion for Research

Since this study is designed to assess benefits of single-dose IV iron administration to pregnant women with iron deficiency anemia, such women will necessarily constitute the participants to be randomized for this trial.

The study is to be carried out in two states of India; thus, participants will be classified as adult female Asians. Pregnant women utilizing facilities classified in the Indian public health system as primary or community health centers will have the opportunity to participate if they meet specified eligibility criteria. No pregnant woman will be excluded because of socio-economic status or other

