In a soon to be published prospective, open label study, FCM was compared to iron isomaltoside (the other formulation to be used in this trial) in patients with iron deficiency anemia primarily unrelated to pregnancy. Hypersensitivity was defined by a standardized set of Medical Dictionary for Regulatory Activities terms. Rates of serious or moderate-to-severe adverse events were low for both products and hypophosphatemia was more common with FCM. A recent study by Wolf et al.⁴³ implied that multiple exposures to FCM may be associated with protracted hypophosphatemia with clinically meaningful sequelae. Prospective data supporting that position are lacking. There is no outcome data in infants of women given FCM during pregnancy.

Based on dozens of clinical trials, FCM, is safe and effective across a broad group of diagnoses associated with iron lack and is widely used in the North America and Europe. In every study in which FCM was compared to oral iron it proved superior in hemoglobin increment, time to target hemoglobin and toxicity profile. FCM has been compared to iron sucrose in prospective studies and shown to have equal or improved efficacy and safety with far fewer visits increasing convenience of both patients and caregivers, decreasing the likelihood of minor infusion reactions, extravasations and costs.

Iron Isomaltoside

Isomaltoside is the newer of the two formulations and the last parenteral iron approved in Europe. Isomaltoside has been renamed ferric derisomaltose by the World Health Organization and the FDA; but for now, the more familiar nomenclature remains in use. Isomaltoside was recently approved under a broad label for iron deficiency in the US with an expected launch in the fourth quarter of 2020. Like FCM, isomaltoside can be administered as 1000 mg in 15 minutes and is actually approved for maximum single doses of 20 mg/kg. As is the case with FCM, there is no evidence that doses of greater than 1000 mg of isomaltoside are advantageous.

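### The safety cohort's IV entry rule asks for the assigned formulation, so a woman known to have received only the other study formulation, and no study tablets, drops out of the section E.5 safety tables

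*Combined protocol and SAP*

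**What the plan says.** Three parts of section E of the combined protocol and SAP bear on this.

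- **Who enters the safety cohort (E.6.C).** A randomized woman enters if she received the provided oral iron tablets or "at least some portion of the one-time, recommended dosage of the assigned IV iron formulation". She must also have given some safety data after treatment.
- **How those who enter are grouped (E.6.C, next sentence).** For all safety analyses, "these participants will be included in the analysis based on treatment actually received, not by randomization arm".
- **What the cohort is used for (E.5).** "All safety analyses will be descriptive based on the safety cohort with no planned formal inference for safety".

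The other two cohorts are defined in the same section. For intent-to-treat (E.6.A), "All randomized study participants will be included using group assignments as randomized". Per-protocol (E.6.B) takes, on the IV side, "All study participants who receive the complete, recommended dosage of the randomly assigned IV iron formulation" within the gestational window. Section E.6 closes with the process: "Assignment of patients into the various cohorts and treatment arms will be determined based on a masked data review prior to initiation of analyses".

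**The concern.** An as-treated safety cohort should admit anyone exposed to a study product and then place her under the product she received. Here the IV entry condition refers back to randomization through the word *assigned*, which is the condition one would expect in a per-protocol cohort. In a trial with two IV products, an infusion of the wrong one is an obvious case for as-treated grouping, and the entry rule removes that woman before grouping can act.

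Such an error is conceivable. Section D has a pharmacist at each community health center match a number to randomization tables and prepare the product, while "neither the PHC staff nor the CHC infusion team will know which IV iron formulation was assigned". The people giving the infusion therefore cannot check it against the assignment.

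At stake are the numerators and denominators of the safety tables for each IV formulation. Appendix C gives a reason to keep the two products apart: in a comparative study of them, "hypophosphatemia was more common with FCM".

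**Working it through.** **1. Reading the rule.** Take a woman assigned one IV formulation, infused only with the other, and known to have been.

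- *Tablet route (E.6.C):* not met if she received no study iron tablets. Section D gives women in the IV arms folic acid and mentions no study oral iron for them, so this route would not normally admit her.
- *IV route (E.6.C):* not met, because she received none of the assigned formulation.
- *As-treated sentence:* it applies to women already in the cohort. It chooses the column and does not widen entry.
- *Masked review (E.6):* it assigns women to cohorts, but no rule is stated that readmits her.
- *Intent-to-treat:* she is counted under the formulation she did not receive. *Per-protocol:* she is excluded. Both are proper for those cohorts, but neither counts her under the product she received.

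The as-treated rule does work in other cases. A woman assigned IV iron who took only the provided tablets is admitted and counted as oral. An infused woman who also received study tablets enters by the tablet route.

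**2. Inputs for size.** From section E.1: about 4,320 randomized 1:1:1, with 7.5% missing birth weight. This reproduces: 1,332 / (1 − 0.075) = 1,440 per arm, and 3 × 1,440 = 4,320. The two IV arms give 2 × 1,440 = 2,880 planned infusions.

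Assumed, because the documents give none of them: a wrong-formulation rate of 0.1% to 1%; a detected fraction of one half or all; a 5% event risk; and a 10% risk in the excluded women.

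**3. Women excluded** = 2,880 × error rate × detected fraction.

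| Error rate | All detected | Half detected |
|---|---|---|
| 0.1% | 2.9 | 1.4 |
| 0.5% | 14.4 | 7.2 |
| 1% | 28.8 | 14.4 |

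Only detected errors count. An undetected one is tabulated as assigned under either wording.

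**4. Per formulation, all detected.** If errors split evenly between the products: 1.4 to 14.4 women. If all errors run one way: 2.9 to 28.8 women for one formulation and none for the other.

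**5. Shift in a formulation's event risk** ≈ (k / 1,440) × (10% − 5%), where k is the number excluded.

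- Even split, all detected: 1.44/1,440 × 5 = 0.005 points, up to 14.4/1,440 × 5 = 0.05 points.
- Even split, half detected: 0.0025 to 0.025 points.
- One direction, all detected: 2.88/1,440 × 5 = 0.01 points, up to 28.8/1,440 × 5 = 0.1 points. Adding the excluded women to the denominator as well, the upper figure is (72 + 2.88)/1,468.8 − 5% = 0.098 points.
- If the excluded women have the same risk as the rest, the shift is zero.

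**6. Yardstick.** The exact (Clopper-Pearson) 95% interval for 72/1,440 = 5% is 3.9% to 6.3%. A shift of 0.1 points lies far inside it.

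**The case against.** The strongest reply is that the intent is plain. The sentence after the entry rule rejects grouping by randomization, and with two IV products a mix-up between them is its natural use. Many analysts would treat *assigned* as loose drafting and place the woman under what she received. That is probably what the authors meant, and it supports the correction. It does not remove the need for one: the item just above in the same section uses the assigned formulation as a strict condition, and a programmer working from the definition would drop her.

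A second reply is that nothing of consequence has been shown. The documents give no error rate and describe no step that would certainly reveal a wrong product. Pharmacist matching is there to prevent one. The Appendix C hypophosphatemia result comes from patients whose anemia was mostly unrelated to pregnancy, and no section confines this trial's phosphate results to the safety cohort. All of this stands and limits the point to a minor one.

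A reader might also infer more than the text supports:

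- *That every infused woman must have had her assigned product to be counted.* She need not if she received study tablets, as with an oral-arm woman later infused after referral.
- *That the excluded woman escapes safety oversight.* She does not. Section H.2 defines serious adverse events for any randomized participant who initiated treatment, and sends them to the DSMB and the adjudicators. The interim safety analysis in E.4 names no cohort, and whether E.5 governs it is unclear. Mortality and several other harms are also secondary outcomes compared by arm under E.3.

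**Conclusion.** The concern holds as a defect of wording with minor impact. E.6.C as written contradicts its own as-treated intent for one kind of woman: known to have been infused only with the other study formulation, and given no study tablets. Her loss is confined to the E.5 tables, which are descriptive.

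The count of about 3 to 29 women and the ceiling of about 0.1 percentage points rest on the assumed error rate, full detection, all errors running one way for the ceiling, and the assumed 10% and 5% risks. No primary result, alpha level, power figure or formal safety inference depends on it. The documents do not support reading this as a material bias in the comparison of the formulations or as a gap in safety monitoring.

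**What to change.** In the E.6.C entry condition, replace *the assigned IV iron formulation* with *either study IV iron formulation*. Keep the sentence on treatment actually received exactly as it is; once entry is widened, it places the woman correctly.

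The cost is one phrase. It needs no new data, no change to sample size or alpha, and no change to the intent-to-treat or per-protocol definitions.
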